9.4.2. Secondary Analyses

Secondary analyses will be performed using the Full Analysis Set. The secondary continuous endpoints (including copper balance, molybdenum balance, and 24-hour urine excretion of copper and molybdenum) will be analyzed using the same methods described for the primary analysis.

9.4.3. Safety Analysis

Safety analyses will be performed using the Safety Analysis Set.

Safety analyses will include all AEs, ECGs, clinical laboratory data, physical examinations, and vital sign measurements using descriptive statistics.

No inferential statistical analyses are planned for the safety parameters of this study. The incidence of AEs and SAEs will be summarized by System Organ Class and Preferred Term for each treatment and overall, and by relationship to study intervention. Adverse events will also be summarized by treatment and overall by severity. Serious AEs and AEs resulting in withdrawal from the study will be listed. Participants having multiple AEs within a category (eg, overall, System Organ Class, Preferred Term) will be counted once in that category. For severity tables, a participant's most severe event within a category will be counted.

Changes from baseline in vital sign measurements and laboratory assessments (eg, chemistry, hematology, coagulation, and urinalysis) will be summarized by treatment. Laboratory parameter values will be graded according to the National Cancer Institute Common Terminology Criteria for Adverse Events (CTCAE). Shift tables by treatment will be produced for these laboratory

parameters. These tables will summarize the number of participants with each baseline grade relative to the reference ranges and changes to the worst highest grade assessed post dose during the study.

Electrocardiogram parameters will be measured at the specified time points as per the SoA (Table 1), including heart rate, PR, RR, QRS, QT, and QTcF intervals. The average of the triplicate ECG readings at the time points collected will be calculated, and changes from pretreatment baseline values will be assessed by each treatment.

All concomitant medications will be coded and summarized using the World Health Organization (WHO) Drug Dictionary.

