1.2. Schema

Figure 1: Study Schematic

- Participants eligible for the study will be enrolled on Day -7 and initiated on a copper- and molybdenum-controlled diet, which will be continued during Treatment Period 1 and Treatment Period 2 when in the CRU, through Day 39.
- Participants will be admitted to the CRU for Treatment Period 1 on Day -8 and may be discharged on Day 9 or remain in the CRU for their own safety or to maintain the integrity of the conduct of the study. Participants who are discharged will be re-admitted on Day 22 or Day 23 for Treatment Period 2 and will remain in house until Day 40. To ensure flexibility, the Outpatient Period may be extended up to an additional 14 days with Investigator approval. In this situation, participants will be given additional investigational product to support daily dosing throughout the Outpatient Period. In such cases, the actual Outpatient Period duration will be recorded and the participant will continue Inpatient Period 2 at Day 23.
- Participants will be administered ALXN1840 at a dose of 15 mg/day on Day 1 through Day 28 and then increase to 30 mg/day on Day 29 through Day 39. During the Outpatient Period, participants will use SMS text messaging to confirm study intervention administration.
- Participants will have 3 intake and output collection periods including:
 - Baseline Day -4 through Day -1
 - Day 1 through Day 8 (I/O for 15 mg)
 - Day 25 through Day 39 (Days 25 through 28, I/O for 15 mg; Days 29 through 39, I/O for 30 mg)
- During these periods all intake (including food and drink) and output (including urine and feces) will be collected and assessed for copper and molybdenum.
- Blood sampling for PK/PD will be as follows:
 - PK/PD collection (24-hour): Days 1, 25, 29, and 39
 - Pre-dose PK/PD sampling days: Days 4 - 7, Days 26 - 28, Days 30 - 38
 - End of Study Visit Day 54 +/- 2 days

Abbreviations: AP = accumulation period; CRU = clinical research unit; EOS = End of Study; I/O = input/output; PD = pharmacodynamic; PK = pharmacokinetic; SS = steady state.

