Vitals sign measurements ^h	X			X			X				X		X									X		X	
12-lead ECG (triplicate)	X			X			X				X		X									X		X	
Adverse events	X		X	X	X	X	X	X	X	X	X	X	X	X	X	X	X	X	X	X	X	X	X	X	
Balance assessments																									
Cu/Mo-controlled meals ^v				X	X	X	X	X	X	X			X	X	X	X	X	X	X	X	X	X			
Light exercise regimen				X	X	X	X	X	X	X		X	X	X	X	X	X	X	X	X	X	X			
Urination and bowel movement monitoring, menstruation check ^s						X	X	X	X	X					X	X	X	X	X	X	X	X			
24-hour urine for Cu and Mo ^w						X	X	X	X	X					X	X	X	X	X	X	X	X			
Feces for Cu and Mo ^x						X	X	X	X	X					X	X	X	X	X	X	X	X			
Other																									
Concomitant medication and non-pharmacologic therapy/procedure	X		X	X	X	X	X	X	X	X	X	X	X	X	X	X	X	X	X	X	X	X		X	

^a Within 42 days of ALXN1840 administration. Details of procedures that may be performed by sites designated as “screening sites” (only in the US) are detailed in Section 8.

^b Participants will be admitted to the clinical research unit (CRU) at least 10 hours prior to enrollment and initiation of copper- and molybdenum-controlled diet.

^c At the CRU’s discretion, participants may remain in the CRU or be readmitted on Day 22 with all procedures starting on Day 23.

^d Unscheduled study visits may occur at any time during the study and may include any study procedure as deemed necessary by the Investigator.

^e Participants are required to return to the CRU Day 54+/-2; participants will be discontinued from ALXN1840 medication by their physician at the latest by the Day 54 follow-up.

^f Discharge from the unit may occur after completion of all procedures on Day 9 and on Day 40 and after the Investigator has reviewed all safety assessment (including safety laboratory tests) and confirmed that the participant is appropriate for discharge.

^g A single outpatient visit or phone call and safety laboratory assessment should occur between Day 14 and Day 18. A phone call may take place on a different day than the blood draw within the Day 14 through Day 18 period.

^h If needed to confirm menopause.

- ⁱ Parameters include age and sex. Race and ethnicity will be collected where permitted by local regulations.
- ^j Wilson disease history will include diagnosis date, method of diagnosis, history of cirrhosis, details of any previous liver biopsies performed, and treatment received.

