9.2. Sample Size Determination

The sample size will be approximately 10 participants which will allow a general characterization of copper balance in response to ALXN1840.

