7.3.2. Adverse Events

The verbatim terms as reported in the CRF by Investigators to identify AEs will be coded using MedDRA Version 22.0 or higher and summarized by primary SOC and PT.

Adverse event toxicity will be evaluated using the National Cancer Institute (NCI) Common Terminology Criteria for Adverse Events (CTCAE) Version 5.0 (published 27 Nov 2017).

Adverse event causality is determined by the Investigator using the following assessment categories: unrelated, or related.

Treatment-emergent AEs are defined as those AEs with onset on or after the first dose of treatment (ie, study drug). Events reported with a partial onset date (eg, month and year are reported but the day is missing) will be considered to be treatment-emergent if it cannot be confirmed that the event onset was prior to the first dose of study drug based on the available date entries.

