7.3.3. Other Safety

7.3.3.1. Analyses for Laboratory Tests

Actual values and changes from treatment Baseline will be summarized descriptively for participants with available data for each laboratory parameter by cohort and overall. Missing laboratory data will not be imputed and only scheduled assessments will be included in by-visit summaries. All data, including that which is only collected at Screening, will be included in data listings. Laboratory measurements will be listed separately by participant, laboratory test, unit, and visit.

Laboratory parameter values will be graded according to the National Cancer Institute Common Terminology Criteria for Adverse Events (CTCAE). Shift tables by treatment will be produced for these laboratory parameters. These tables will summarize the number of participants with each baseline grade relative to the reference ranges and changes to the worst highest grade assessed post dose during the study.

Summary results for shift will include the count and percentage of participants within each shift category by scheduled visit. Laboratory values outside the normal range will also be summarized and assessed for trends indicating a safety signal. Additionally, a summary and listing of liver enzyme elevation will be presented and an evaluation of drug-induced serious hepatotoxicity plot will be created.

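### AE incidence and worst-grade laboratory shifts by dose are planned as crude participant counts, so they are confounded with unequal time at risk (28 to 42 days at 15 mg, 11 at 30 mg) and depend on an unstated attribution window

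*Protocol*

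**What the plan says.** Protocol 9.4.3 commits to by-treatment AE tables: "The incidence of AEs and SAEs will be summarized by System Organ Class and Preferred Term for each treatment and overall". A participant with several events in a category counts once, and laboratory shift tables are also by treatment. In a single-arm escalation, treatment most naturally means dose, and SAP 7.4.1 itself glosses it that way. The same section adds: "No inferential statistical analyses are planned for the safety parameters of this study".

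The schedule in Protocol 1.2 is "15 mg/day on Day 1 through Day 28 and then increase to 30 mg/day on Day 29 through Day 39". The outpatient stretch, which falls entirely at 15 mg, may be lengthened by up to 14 days. While participants are out of the unit, Protocol 1.3 (footnote g) requires little contact: "A single outpatient visit or phone call and safety laboratory assessment should occur between Day 14 and Day 18".

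AEs are collected until the End of Study visit, Day 54 ± 2 (Protocol 8.3.1 and 1.3). SAP 7.3.2 gives the treatment-emergent window a start but no end: "Treatment-emergent AEs are defined as those AEs with onset on or after the first dose of treatment". The by-treatment shift tables in SAP 7.3.3.1 run to "changes to the worst highest grade assessed post dose during the study", which is a whole-study window.

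The SAP does not carry the by-dose AE tables through. Section 7 presents results by cohort (treatment experienced or naïve) and overall, and the denominators in 7.3.2 are the Safety Set or the treatment cohort. SAP 4.1 nevertheless declares no changes from the protocol.

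**The concern.** Every participant is meant to pass through 15 mg and then 30 mg. The two doses differ in how long participants are exposed and in how closely they are watched. A table giving the percentage with each event by dose invites a direct reading across columns, and those columns have different amounts of time behind them. Nothing planned supplies the missing denominator.

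The safety objective names both doses, and the study is meant to inform how they are used. A reader who sees a lower crude percentage under 30 mg could take it as better tolerability when it reflects a shorter window. The size of any apparent difference also turns on where events after the last dose are counted, which neither document says.

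**Working it through.** **Inputs from the documents**
- 15 mg, Days 1–28: 28 − 1 + 1 = 28 days, matching the approximately 28 days in Protocol 4.1. With the full extension, 28 + 14 = 42.
- 30 mg, Days 29–39: 39 − 29 + 1 = 11 days, all inpatient.
- Exposure ratio: 28/11 = 2.55; 42/11 = 3.82.
- Scheduled inpatient days at 15 mg: Days 1–9 (9) plus Days 23–28 (6) = 15. Outpatient: 13 of 28 (46%) by default, up to 27 of 42 (64%), and none if the participant stays in the unit (Protocol 4.1).
- 30 mg window if run to End of Study: 54 − 29 + 1 = 26 days (24 to 28 with the ± 2).

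**Assumption.** The documents give no AE rate. I take the same constant daily hazard at both doses and range the 28-day incidence p over 10%, 30% and 50%. Then λ = −ln(1 − p)/28, and incidence over T days is 1 − exp(−λT).

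| 28-day incidence (15 mg) | λ per 100 days | 30 mg, 11 days | Ratio 28:11 days | 15 mg, 42 days | Ratio 42:11 days | 30 mg, 26 days | Ratio 28:26 days | Ratio 42:26 days |
|---|---|---|---|---|---|---|---|---|
| 10% | 0.38 | 4.1% | 2.47 | 14.6% | 3.61 | 9.3% | 1.07 | 1.57 |
| 30% | 1.27 | 13.1% | 2.29 | 41.4% | 3.17 | 28.2% | 1.06 | 1.47 |
| 50% | 2.48 | 23.8% | 2.10 | 64.6% | 2.71 | 47.5% | 1.05 | 1.36 |

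With an 11-day window, even a doubled hazard at 30 mg would show 7.9%, 24.4% and 42.0%, each below the 28-day figure at 15 mg. With the window run to Day 54 the artefact nearly vanishes on the unextended schedule. The attribution rule therefore matters as much as the denominator.

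**Do the planned exposure summaries fill the gap?** SAP 7.3.1 summarizes exposure overall and for the periods of 7.2.1. Those are Days 1–8 and 25–28 (8 + 4 = 12 of 28 days at 15 mg) and Days 31–35 and 36–39 (5 + 4 = 9 of 11 days at 30 mg). Person-time by dose cannot be read from them.

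**Laboratory draws.** Scheduled post-baseline chemistry and hematology draws number about 4 at 15 mg (Day 8, Days 14–18, Day 23, Day 28). There are about 2 at 30 mg (one around Days 30–36, which the broken table does not place exactly, and Day 40), or 3 with End of Study. The ratio is 4/3 to 4/2, or 1.3 to 2.0, smaller than the exposure ratio.

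**Latency.** Protocol Table 3 places transaminase elevations usually at 3 to 6 weeks, about Days 21–42. On the unextended schedule that covers all 11 days at 30 mg but only the last 8 of 28 at 15 mg (Days 21–28). Constant hazard is therefore only a yardstick here.

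**The case against.** The strongest case against runs as follows.
- **Only one document plans AE tables by dose.** No AE table in SAP 7.3.2 is split by dose. This stands as a fact, but SAP 4.1 declares no change, so the Protocol commitment remains and the two must be reconciled.
- **No safety comparison of doses is pre-specified.** The dose-response objective concerns copper balance, and safety is descriptive. This stands and lowers the priority.
- **The biases do not all point one way.** Lighter outpatient observation would lower 15 mg counts. Latency under a fixed order would push some events towards 30 mg. Both stand. Person-time does not remove either, and for late-onset events a per-day rate could overstate 30 mg.
- **Crude percentages are not all the SAP gives.** It also plans event counts, participant listings of AEs, and shifts by scheduled visit. With about 10 participants, listings show onset directly. This helps a careful reader, but by-visit shifts do nothing for AEs and a listing is not a denominator.

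A reader might infer that 30 mg will look about half as toxic as 15 mg and that the dose contrast is driven by observation time. The documents do not support that. It needs an 11-day cut-off that the plan does not contain, and it ignores the opposing biases. Nor is two-thirds of 15 mg time being outpatient the norm. It approximates the ceiling under full extension, and that stretch still includes one contact and one laboratory draw.

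**Conclusion.** The point holds as confounding. Crude by-dose AE percentages, as Protocol 9.4.3 promises them, mix dose with time at risk and closeness of observation. Under equal constant hazard and a 28-day incidence of 10% to 50%, the spurious 15:30 mg ratio is 2.1 to 2.5 (2.7 to 3.6 with extension) if 30 mg is limited to its 11 dosing days. It is 1.05 to 1.07 (1.36 to 1.57 with extension) if 30 mg absorbs everything to Day 54. The net direction in the real data cannot be predicted from the documents.

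For laboratory shifts the first defect is that worst grade is defined over the whole study, so its by-dose window is undefined; unequal draw counts come second. A reader might infer that the planned shifts are biased 4 draws to 2, but the plan sets no such split.

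Priority is modest: safety is descriptive and not primary, and "The sample size will be approximately 10 participants".

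**What to change.** All changes are to analysis wording only.
- Reconcile Protocol 9.4.3 (by treatment) with SAP 7.3.2 (by cohort and overall), and declare any difference in SAP 4.1.
- Assign each AE to the dose in effect at onset, in three bands: 15 mg, 30 mg, after last dose. Use actual dosing dates, because an extended participant's nominal Day 29 can be the 43rd actual day (29 + 14).
- In each band, report events, and participants with events, per participant-time. The denominator is participants who actually received that dose. Protocol Table 4 lets some stay at 15 mg, which would give them 39 days there (53 with extension) and none at 30 mg. For participants with events, stop time at the first event in the band; otherwise equal hazards still give unequal rates (50%/28 = 1.79 against 23.8%/11 = 2.16 per 100 days).
- Add a supportive table restricted to scheduled inpatient days: Days 1–9 and 23–28 against Days 29–39.
- Limit any by-dose worst-grade shift to values drawn in that dose's window, state where the Day 40 draw belongs, and show draws per participant. Use the by-visit shifts already planned for any dose comparison.
- State that dose remains confounded with time on treatment.

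The cost is SAP wording and a few table columns, since dosing, interruption and AE dates are already recorded. The downside is imprecision: about 10 × 11 = 110 participant-days at 30 mg.

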9.4.4. Pharmacokinetic, Pharmacodynamic, and Biomarker Analyses

For PK, PD, and biomarker endpoints, analyses will be performed using the PK/PD Analysis Set. The following plasma PK parameters will be calculated for total molybdenum and PUF molybdenum (as surrogate measures of ALXN1840 PK) using noncompartmental methods with Phoenix® WinNonlin® (Certara USA Inc., Princeton, New Jersey) Version 8.0 or higher or SAS Version 9.3 or higher (SAS Institute Inc., Cary, North Carolina), as applicable. Calculations will be based on the actual sampling times recorded during the study.

- Time delay between the time of dosing and time of appearance of molybdenum concentration (T_{lag}) in plasma
- Maximum observed concentration (C_{max})
- Time to maximum concentration (t_{max})
- Trough (predose) concentration observed at the start of the dosing interval (C_{trough})
- Area under the plasma concentration versus time curve (AUC) from time 0 to the last quantifiable concentration (AUC_t)
- AUC over the dosing interval (AUC_{tau})
- Accumulation ratio (AR) calculated as:

For 15 mg/day:

- $C_{max,Day25}/C_{max,Day1}$
- $C_{trough,Day26}/C_{trough,Day2}$
- $AUC_{tau,Day25}/AUC_{tau,Day1}$

For 30 mg/day:

- $C_{max,Day39}/C_{max,Day29,adjusted}$
- $C_{trough,Day40}/C_{trough,Day30,adjusted}$
- $AUC_{tau,Day39}/AUC_{tau,Day29,adjusted}$

Note: total molybdenum and PUF molybdenum concentration-time profiles on Day 28 after the last 15 mg ALXN1840 dose will be extrapolated to Day 29 (0-24 hr) and subtracted from the observed Day 29 concentration-time profiles after the first 30 mg

ALXN1840 dose for the estimation of the $C_{\max, \text{Day}29, \text{adjusted}}$, $C_{\text{trough}, \text{Day}30, \text{adjusted}}$, and $AUC_{\tau, \text{Day}29, \text{adjusted}}$.

- Apparent terminal phase elimination rate constant (λ_z)
- Terminal elimination half-life ($t_{1/2}$)
- Apparent total body clearance (CL/F) of ALXN1840 from plasma
- Apparent volume of distribution (V_d/F).

Additional plasma PK parameters may be calculated if deemed appropriate.

Plasma concentrations of total molybdenum and PUF molybdenum vs. time data will be presented in a data listing by participant. Plasma concentration data will be summarized separately by analyte and time point for each treatment by day using the following descriptive statistics: number of participants, arithmetic mean, geometric mean (GM), SD, coefficient of variation (CV), GMCV, median, minimum, and maximum. Mean plasma concentration versus scheduled time profiles will be presented in figures on both linear and semilogarithmic scales. Individual plasma concentration versus actual time profiles will be presented similarly.

Pharmacokinetic parameters derived from plasma concentrations of total molybdenum and PUF molybdenum will be presented in data listings and summarized separately using the following descriptive statistics: number of participants, arithmetic mean, GM, SD, arithmetic CV, GMCV, median, minimum, and maximum. Geometric mean and geometric CV will be presented for C_{\max} and AUCs only.

For PD (total and PUF copper and LBC) and biomarker endpoints (ceruloplasmin, ceruloplasmin-bound copper), concentration-time data will be listed and summarized with descriptive statistics and plotted. The same analyses will be conducted on the absolute and percent changes from baseline of these concentration-time data.

9.5. Interim Analyses

Marketing Authorisation Application(s) may be submitted before all patients complete the Treatment Periods; therefore, interim analyses of safety and efficacy data may be performed to support these submissions. These analyses will be descriptive only; they will not include formal hypothesis testing and will not be used to adapt the study. Full details will be provided in the SAP.

9.6. Data Monitoring Committee

There will not be a Data Monitoring Committee, but provision is included for an SRC (Section 9.7).

9.7. Safety Review Committee (SRC)

A SRC, composed of a minimum of the Investigator, Alexion Medical Monitor, and Alexion Safety Physician, will meet at the end of 15 mg/day dosing to confirm proceeding to 30 mg/day and as necessary based on any emerging safety concerns as described in Section 6.6.

10. SUPPORTING DOCUMENTATION AND OPERATIONAL CONSIDERATIONS

10.1. Regulatory, Ethical, and Study Oversight Considerations

10.1.1. Regulatory and Ethical Considerations

- This study will be conducted in accordance with the protocol and with the following:
 - Consensus ethical principles derived from international guidelines including the Declaration of Helsinki and Council for International Organizations of Medical Sciences (CIOMS) International Ethical Guidelines
 - Applicable International Council for Harmonisation (ICH) Good Clinical Practice (GCP) Guidelines
 - Applicable laws and regulations
- The protocol, protocol substantial amendments, ICF, IB, and other relevant documents (eg, advertisements) must be submitted to an IRB/IEC by the Investigator and reviewed and approved by the IRB/IEC before the study is initiated.
- Any substantial amendments to the protocol will require IRB/IEC approval before implementation of changes made to the study design, except for changes necessary to eliminate an immediate hazard to study participants.
- The Investigator will notify the IRB/IEC of deviations from the study protocol or GCP as defined by UK legislation as a serious breach or as required by IRB/IEC procedures.
- The Investigator will be responsible for the following:
 - Providing written summaries of the status of the study to the IRB/IEC annually or more frequently in accordance with the requirements, policies, and procedures established by the IRB/IEC
 - Notifying the IRB/IEC of SAEs or other significant safety findings as required by IRB/IEC procedures
 - Providing oversight of the conduct of the study at the site and adherence to requirements of 21 Code of Federal Regulations (CFR), ICH guidelines, the IRB/IEC, Directive 2001/20/EC, European regulation 536/2014 for clinical studies (if applicable), and all other applicable local regulations

